#### 8.5 Site-level Poolability

Poolability of data from multiple sites will be verified by examining the primary endpoint among sites. Site-level poolability will be considered appropriate provided that this measure is similar among sites. It is expected that some sites may have too few patients to provide reasonable site-level estimates of the primary endpoint. Pooling of this information will be explored based on hospital size (annual discharge and number of beds), type of hospital (community versus teaching), and other group-wise strategies. Should one or more sites differ from the rest, then subsequent analyses will include the discriminating covariate or a covariate to distinguish between the unusual site(s) and those sites that are considered poolable.

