## 8.0 Statistical Considerations

### 8.1 Hypothesis to be Tested

The primary hypothesis will assess the treatment success rate evaluated at 12 months for the Zenith® p-Branch™. [REDACTED]

[REDACTED] a [REDACTED] performance goal of 80% has been established. The performance goal will be said to have been met provided that the null hypothesis is rejected in favor of the alternative with a one-sided exact binomial test at the 0.05 level. The null ( $H_0$ ) and alternative ( $H_A$ ) hypotheses are expressed as follows, where  $\pi$  is the proportion of patients treated with the Zenith® p-Branch™ with treatment success at 12 months:

Null Hypothesis: The 12-month treatment success rate for patients treated with the Zenith® p-Branch™ does not meet the performance goal (80%).

$$H_0: \pi \leq 80\%$$

Alternative Hypothesis: The 12-month treatment success rate for patients treated with the Zenith® p-Branch™ meets the performance goal (80%).

$$H_A: \pi > 80\%$$

The safety and effectiveness of the Zenith® p-Branch™ will be established if the null hypothesis is rejected in favor of the alternative at a type I error rate of 0.05 (one-sided). This analysis will be performed on the intent-to-treat population.

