### 8.2 Statistical Analysis

Statistical analyses will be performed using SAS® for Windows® (release 9.3 or higher) or other widely accepted statistical software. Descriptive summaries will be provided where appropriate for each of the primary and secondary endpoints. In general, summaries will be completed over the total population. Continuous variable summaries will include the number of subjects (N), mean, standard deviation, minimum, and maximum. Categorical variable summaries will include the frequency and percentage of subjects who are in the particular category. Survival analysis techniques such as Kaplan-Meier or Cox

Proportional Hazards will be incorporated if censoring of data occurs.

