### 8.3 Sample Size Calculation

[REDACTED]  
[REDACTED]  
[REDACTED]  
[REDACTED] With a clinically relevant margin of 10%, [REDACTED]  
[REDACTED]  
[REDACTED]

[REDACTED] Thirty-four (34) patients are necessary to assess the primary hypothesis, under an expected 12-month treatment success rate of 97.4% [REDACTED]  
[REDACTED], with a one-sided exact binomial test, at a Type I error rate of 0.05 and a power of 0.8. A sample size of 80 patients will be enrolled to account for possible loss to follow-up while also ensuring sufficient use of both p-Branch graft configurations.

No more than 20 patients (i.e., 25% of total enrollment) will be enrolled at any one site [REDACTED]  
[REDACTED]  
[REDACTED]

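### Does section 8.5 need a criterion for sites that differ, and a stated status for the covariate it then calls for?

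*Combined protocol and SAP*

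**What the plan says.** Section 8.5 examines the primary endpoint among sites. Its criterion is: "Site-level poolability will be considered appropriate provided that this measure is similar among sites". It expects some sites to be too small for a useful estimate and proposes grouping them by hospital size, hospital type or other schemes. If a difference appears, the instruction is: "Should one or more sites differ from the rest, then subsequent analyses will include the discriminating covariate". The alternative it allows is a covariate that separates the unusual sites from the poolable ones. It states no test, threshold, minimum site size or model.

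Section 8.1 sets the decision rule. The 80% performance goal is met if the null hypothesis is rejected "with a one-sided exact binomial test at the 0.05 level", and "This analysis will be performed on the intent-to-treat population". No covariate and no poolability condition appear there.

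Section 8.2 adds: "In general, summaries will be completed over the total population". It names "Survival analysis techniques such as Kaplan-Meier or Cox" regression for censored data. Section 8.4 allows endpoints to be modelled on covariates when missing data are imputed. Section 6.3.2 makes the secondary endpoints descriptive. Section 8.3 expects 97.4% success, enrols 80 patients and caps any one site at 20.

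**The concern.** The instruction to include a covariate is mandatory, but the event that triggers it is undefined. The covariate would also be picked from the outcome it then adjusts, in an unblinded study whose section 6.5 lists a prospectively defined analysis plan among its safeguards against bias.

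There is a practical difficulty too. With so few failures expected, one of the compared groups may have none. The maximum-likelihood log odds ratio or log hazard ratio is then infinite, so the plan would require an estimate that ordinary software cannot give. Section 8.5 also does not say that such results are secondary to the test in 8.1. If they could override that test, the trial's claim would depend on an after-the-fact judgement about sites.

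**Working it through.** **Inputs.** From the plan: N = 80, expected success 0.974 and the site cap of 20 (section 8.3); goal 0.80 and one-sided level 0.05 (section 8.1). The visible text gives no group sizes, and some lines after the site cap in 8.3 are blacked out. Hospital-group splits of 40/40, 50/30 and 60/20 are therefore assumptions, as are the three triggers tried below. The plan states no poolability figure that could be reproduced.

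**Step 1: the decision rule.** For X ~ Bin(80, 0.80), P(X ≥ 70) = 0.0565 and P(X ≥ 71) = 0.0287. The goal is therefore met with 71 or more successes. At 0.974 the power is 0.99996. Nothing in 8.5 enters this calculation.

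**Step 2: how sparse the failures are.** Expected failures are 80 × 0.026 = 2.08, and P(no failures) = 0.974^80 = 0.1215. For groups of size a and b, P(at least one group has no failures) = 0.974^a + 0.974^b − 0.974^80:
- 40/40: 0.3486 + 0.3486 − 0.1215 = 0.576
- 50/30: 0.2679 + 0.4537 − 0.1215 = 0.600
- 60/20: 0.2058 + 0.5904 − 0.1215 = 0.675

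**Step 3: how often the rule fires, and what then happens.** For each pair of failure counts (x, y), take Bin(x; a, 0.026) × Bin(y; b, 0.026). Sum over the pairs that meet the trigger, then over those in which x or y is zero. This is exact enumeration with no true group difference.

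| Trigger | Fires (40/40, 50/30, 60/20) | A group has no failures, given it fires |
|---|---|---|
| Any unequal observed rates | 69.8%, 87.8%, 83.6% | 65%, 55%, 66% |
| Two-sided Fisher p<0.10 | 0.3%, 1.5%, 2.8% | 98%, 81%, 69% |
| Two-sided Fisher p<0.05 | 0.04%, 1.2%, 0.8% | 98%, 97%, 36% |

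The highest conditional figures belong to events that almost never occur. The unequal-rates trigger is an implausibly strict reading of similarity: at 50/30 it fires essentially whenever there is any failure (1 − 0.1215 = 0.878).

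**Step 4: a real difference, 60/20, same overall rate.**
- With 60 patients at 99.87% and 20 at 90%, p<0.10 fires in 59% of trials, and 96% of those have a group without failures. Much of this is built in, because 0.99867^60 = 0.92.
- With 98.5% and 94.1%, p<0.10 fires in 19% (69% with such a group) and p<0.05 in 9% (49%).

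**Step 5: the other branch of 8.5, unusual site against the rest.** This used 20,000 simulated trials for each of six assumed site layouts, at 0.974 with no true difference. The contrast between the worst site and the rest has no finite estimate in 31% to 38% of trials with at least one failure. If the worst site must also reach Fisher p<0.05, the range is 14% to 64%.

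**Step 6: lower success rates.** With unequal observed rates as trigger and splits as in Step 3, the share with a failure-free group falls to 28%, 27% and 42% at a true 95%, and to 3%, 5% and 13% at 90%.

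**The case for a change.** The best case for a change is that it would be cheap and the gap is genuine. Section 8.5 makes the covariate compulsory, leaves the groupings open and gives no criterion. Step 3 shows that the choice of criterion alone moves the firing rate from under 3% to as much as 88%. One or two sentences could say that the 8.1 test decides whatever the site comparison shows, and that group results are supportive and given as failures over patients with exact intervals. That would also prevent argument over whether an unadjusted report departs from the plan.

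The textual gap stands, and so does the sparseness. Three parts do not carry the weight put on them:
- The covariate is often, but not generally, inestimable. The share runs from 14% to 98% across the assumed triggers and groupings at 97.4%.
- The difficulty is confined to ordinary maximum likelihood on a sparse binary or time-to-event outcome. Section 8.5 names no model. Penalised likelihood or exact methods give estimates with an empty cell, and section 8.2 does not tie the analyst to one package. A continuous outcome such as change in aneurysm size takes a group covariate without trouble.
- A covariate is not foreign to the plan, since section 8.4 also foresees modelling endpoints on covariates.

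The suggested sentences would mainly write down the natural reading of 8.1 and 8.5 together.

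**Conclusion.** No change is needed. Section 8.5 leaves out a criterion and a label, and a competent analyst can supply both without affecting what the trial concludes. The decision on the 80% goal is the exact test on all intent-to-treat patients: 71 or more of 80, type I error 0.0287, power above 0.999 at 97.4%. It stays the same whether or not sites are called similar. The secondary endpoints carry no inference that a site covariate could distort. What remains is supportive: tabulate failures over patients by hospital group, and use a penalised or exact method if a model is wanted.

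The power and sparseness figures assume the plan's 97.4%, and all counts assume 80 evaluable patients. The group splits, site layouts and triggers are assumptions, because the visible text gives none. The conclusion does not depend on them, since no value of those inputs enters the 8.1 test. A sentence labelling the site results as supportive would do no harm, but it is optional.

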#### 8.6 Limitations of the Study

This study is designed as a single-arm study without a concurrent control group. The hypothesis of the study involves meeting a performance goal derived from previous clinical study results and literature. In the unlikely event that major changes in medical practice have occurred since those studies were performed, the determination of whether or not the device met the performance goal may be questioned.

Study results may be generalizable only to the types of patients enrolled in the study, which is expected to represent the Medicare patient population based on age. For a previous study, with similar inclusion and exclusion criteria, the mean was 75 years (IDE # G040063).

### 9.0 Deviations from Clinical Investigation Plan

Investigators are not allowed to deviate from this clinical investigation plan (CIP) without prior authorization by the Sponsor except under emergency situations when necessary to preserve the rights, safety, and well-being of human subjects.

Deviations and non-compliances will be recorded together with an explanation. Deviations or non-compliances that impact the rights, welfare, or safety of patients shall be reported to the Sponsor and IRB as soon as possible.

If appropriate, corrective and preventive actions will be discussed by the sponsor, investigator, and/or the IRB to determine a suitable course of action.

## **10.0 Data Collection and Reporting**

### **10.1 Electronic Case Report Forms**

Patient data will be collected and entered by trained personnel at the investigative site into an electronic Case Report Forms (eCRFs) through an electronic data capturing (EDC) system.. This is a secure, web-based system that allows those with permission to access data from any location at any time. Source data are to be retained for data entered into the EDC system. Data obtained and simultaneously entered into the EDC system may also serve as source documentation (e.g. telephone follow-up). Site personnel are required to have unique login names and passwords in order to enter patient data. In accordance with 21 CFR Part 11, the EDC system creates a secure, computer-generated, time-stamped audit trail to record the date and time of operator entries and actions that create, modify, or delete electronic records.

### **10.2 Data Reporting**

Annual progress reports and a final report at the conclusion of the clinical investigation (or if the study is terminated early) will be submitted by the investigators and the Sponsor to the regulatory bodies and IRBs as required by local regulations.

This clinical study shall be registered with the National Institutes of Health (NIH) National Library of Medicine's (NLM) ClinicalTrials.gov website. Registration and reporting of results shall be submitted in accordance with Section 801 of the Food and Drug Administration Amendments Act.

## **11.0 Data Management and Quality Assurance**

### **11.1 Data Entry and Quality Assurance**

Each principal investigator or appropriately trained designee shall enter the clinical data into the EDC on standardized eCRFs. Investigators will provide all applicable clinical data and documentation to the

sponsor. Patient data and documents pertaining to the study will be kept and archived by the sponsor. Data will be reviewed for missing data, data consistency, and reasonableness of responses.

Discrepancies will be resolved through a formal query process involving direct contact with investigators or research coordinators. The data coordinating center is responsible for database management, data verification, data archiving and data retention.

Pertinent imaging (pre-procedure, procedure, and follow-up) will be sent to MED Institute, which will coordinate shipment of imaging for independent analysis.

## 11.2 Data Monitoring Arrangements

The conduct of the clinical study will be supervised through a process of centralized and on-site monitoring. The Data Coordinating Center will remotely monitor the study for data completeness and for adverse events. On-site monitoring will be implemented as necessary throughout the course of the study. The investigator/institution will provide direct access to source data/documents for study-related monitoring, audits, IRB review and regulatory inspection. Written procedures for monitoring the investigation are maintained by the monitors and can be found in Appendix B.

# 12.0 Safety Monitoring and Procedures for Reporting Adverse Events

## 12.1 Safety Monitoring

A Data Safety Monitoring Board (DSMB) consisting of independent physicians and a least one independent statistician, who are not investigators in the investigation, and who do not have a perceived conflict of interest with the conduct and administration of the investigation, will be convened on a regular basis to evaluate investigation progress and review adverse events.

An independent Clinical Events Committee (CEC) consisting of physicians, who are not investigators in the investigation, and who do not have a perceived conflict of interest with the conduct and administration of the investigation, will be established to adjudicate clinical events reported during the investigation. This adjudication will be performed to assess whether the events were due to a pre-existing or unrelated condition, or were procedure-related, technique-related, and/or device-related.

Regularly scheduled review/monitoring of all patient data will be conducted at the Data Coordinating Center, in part, for identification of adverse events and assurance that they are correctly reported to the DSMB and CEC.

## 12.2 Adverse Event Reporting

Adverse events are to be reported to the Data Coordinating Center using the appropriate eCRF. In cases of adverse device effects or serious adverse events, completed forms should be submitted to the Data Coordinating Center as soon as possible upon knowledge of the event.

The Data Coordinating Center will review the information submitted for possible reporting to the Sponsor. The Sponsor shall, if required according to applicable regulations, report the event to the appropriate Regulatory Authority. The Principal Investigator or designee will notify their IRB of applicable events according to institutional guidelines. If indicated, all investigators and sites will be notified of applicable by the Sponsor.

## 13.0 Early Termination or Suspension of the Investigation

Any decision to suspend enrollment or terminate the clinical study, either completely or at one or more clinical sites, will be made by the Sponsor and, if appropriate, the local IRB. If a decision is made to terminate the study, all patients already treated will be followed for 60 months following the procedure. Regulatory authority(ies) and/or IRB(s) will be notified as required by local regulations.

## 14.0 Ethical Considerations

The investigation will be conducted in accordance with the ethical principles that have their origin in the Declaration of Helsinki and in compliance with ISO 14155, ICH GCP, 21 CFR 812, and any regional or national regulations, as appropriate.

The investigator is responsible for obtaining approval of this clinical investigation by the relevant IRB at their associated institution and the clinical investigation will not begin until a favorable opinion of the IRB .The Sponsor must be provided with a copy of this approval prior to delivery of the study device. The investigator is responsible for complying with requirements imposed by an IRB and/or regulatory authority. Furthermore, the Sponsor and the investigator will ensure that local regulations concerning data protection are followed.

Written informed consent must be obtained from all patients, or the patients' legally-authorized representative, in accordance with applicable regulatory requirements prior to enrollment in the study.

## 15.0 Publication Policy

Publication policy, rights, and obligations for this investigation have been negotiated, detailed, and defined in the Investigation Contractual Documents with the investigation sites and investigators.

## **16.0 Trial Administration and Investigators**

### **16.1 Approvals and Agreements**

The Sponsor, national principal investigator, and the principal clinical investigators for each site shall agree to this document and any modifications. A justification for any modifications will be documented. Approval and agreement will be indicated by signing and dating the appropriate document.

### **16.2 Investigators**

To see a complete list of the Sponsor, Manufacturer, Data Coordinating Center, and Monitor, along with their contact information, please refer to Appendix A. A complete list of the national principal investigator, principal investigators and coordinating investigators, and core laboratory, along with their qualifications and contact information, will be updated and maintained by the Data Coordinating Center.

### **16.3 Insurance**

The devices are covered by the Sponsor's product liability insurance, and a clinical investigation insurance policy will be taken out according to local requirements. Insurance for the study will be obtained by the sponsor prior to patient enrollment.

[REDACTED]

[REDACTED]

[REDACTED]

[REDACTED]

[REDACTED]

[REDACTED]

[REDACTED]

A high-contrast, black and white image showing a series of abstract, geometric shapes. The shapes are composed of thick, solid black lines and rectangles, set against a white background. The overall effect is minimalist and graphic, resembling a stylized architectural drawing or a abstract representation of a city skyline.

1. **What is the name of the organization?**

1

5

---

**APPENDIX B – Written Procedures for Monitoring Investigations**

---

### **Written Procedures for Monitoring Clinical Investigations**

**A. Selection of the monitor.**

Designated by the Sponsor to oversee the investigation, the monitor may be an employee of Cook, an employee of a monitoring organization (CRO) or an independent contractor or consultant. The monitor shall be qualified by training and experience to monitor the investigation in accordance with all applicable regulations and standards for conducting clinical investigations.

**B. General duties of the monitor.**

The monitor must ensure that the investigation is conducted in accordance with:

1. The signed investigator agreement.
2. The Clinical Investigation Plan (CIP)/protocol.
3. Any conditions imposed by the IRB or Regulatory Authority.
4. The requirements of the applicable regulations and standards.

**C. Reports by the monitor to the Sponsor.**

1. Any noncompliance with the items listed above. In the event that the investigator is not complying with the requirements outlined above, it is the Sponsor's responsibility to secure compliance.
2. Any adverse events or effects that are potentially reportable to a Regulatory Authority.

**D. Initiating the investigation.**

Prior to initiating any clinical use of the device, the monitor and/or a Sponsor representative will participate in a pre-investigation or initiation visit with each investigative site.

At a minimum, the following items shall be addressed during the site initiation visit:

- Provide training to investigator on his/her responsibilities per the investigator agreement, applicable laws, regulations and standards; and
- Provide training to investigator that the IRB approval letter and informed consent/patient information is on file before initiation of the clinical investigation.

Additionally, training may be provided to the investigator on:

- The regulatory status of the device/product(s) and the requirements for the accountability of same;
- The nature of the CIP;
- The requirements for an adequate and well-controlled clinical investigation;
- His or her obligation to obtain informed consent in accordance with applicable regulations;
- His or her obligation to ensure continuing review of the clinical investigation by the IRB in accordance with conditions of approval and applicable regulations and to keep the Sponsor informed of such IRB approval and subsequent IRB actions concerning the investigation;
- The importance of access to an adequate number of suitable patients to conduct the investigation;
- The importance of adequate facilities for conducting the clinical investigation; and
- The importance of sufficient time from other obligations to carry out the responsibilities to which the investigator is committed by applicable regulations.

E. During the course of the investigation, at the direction of the Project Manager, the monitor should visit the site frequently enough to ensure that:

- The facilities and research staff used by the investigator continue to be acceptable for purposes of the clinical investigation;
- The applicable version of the CIP and agreements are being followed;
- Changes to the CIP, informed consent/patient information have been approved by the IRB and/or reported to the Sponsor and the IRB;
- Accurate, complete, and current records are being maintained;
- Accurate, complete, and timely reports are being made to the Sponsor and IRB; and
- The investigator is carrying out the agreed-upon activities and has not delegated them to other previously unspecified staff.

As appropriate, the following tasks could be performed during periodic visits:

- Device/product accountability review;
- Adverse event review to ensure that events are appropriately reported within the time periods required by the Sponsor, CIP, IRB, and applicable regulatory requirements; and
- Source data verification per the monitoring plan to determine that :

- Informed consent/patient information has been documented in accordance with applicable regulations and expectations of local IRB;
- The information recorded in the CRFs (paper or electronic) is complete, accurate, and legible;
- There are no omissions in the CRFs of specific data elements, such as the administration to any patient of concomitant test articles or the development of an intercurrent illness;
- Missing visits or examinations are noted; and
- Patients failing to complete the clinical investigation and the reason for each failure are noted.

F. Records of the monitor.

The monitor shall prepare and maintain records of each initiation visit and each periodic visit, general site contact, or discussion. These will include:

1. Date, name and address of the investigator, and names of other staff members present at each meeting.
2. A summary of the findings of the visit.
3. A statement of any action taken by the monitor or investigator to correct any deficiencies noted.
4. The monitor shall immediately notify the Sponsor of any conditions of non-compliance with the Clinical Investigation Plan, conditions of IRB or Regulatory Authority approval, or the applicable regulations.

---

